# BRIEF SUMMARY OR ABSTRACT OF THIS PHASE II CLINICAL TRIAL STUDY PROTOCOL

In the United States, patients dependent upon parenteral nutrition (PN) receive parenteral lipid emulsions composed of soybean oils. Lipids are necessary in PN dependent patients due to their high caloric value and essential fatty acid content. They have been implicated in predisposing patients to PN associated liver disease (PNALD). Phytosterols such as those contained in soybean oils are thought to have a deleterious effect on biliary secretion. Accumulation of lipids in the hepatic Kupffer cells may further impair liver function.

Children requiring prolonged courses of PN are at risk for developing PNALD. It is s hypothesized that although omega-6 fatty acid emulsions prevent fatty acid deficiency, they are not cleared in a manner similar to enteral chylomicrons and therefore accumulate in the liver and result in steatotic liver injury. It is further hypothesized that a fat emulsion comprised of omega-3 fatty acids (i.e., fish oil) such as Omegaven® would be beneficial in the managemet of steatotic liver injury by its inhibition of de novo lipogenesis, the reduction of arachidonic acid-derived inflammatory mediators, prevention of essential fatty acid deficiency through the presence of small amounts of arachidonic acid, and improved clearance of lipids from the serum. Animal studies have shown that IV fat emulsions (IFE) such as fish oil that are high in eicosapentaenic and docashexaaenoic acid reduce impairment of bile flow which is seen in cholestasis caused by conventional fat emulsions. Furthermore, it is hypothesized that intravenous omega three fatty acids will be well tolerated and might reduce the inflammatory effect in the liver of prolonged PN exposure and could potentially reverse any hepatic dysfunction due to PN/IFE use. By administering Omegaven® in place of conventional phytosterol/soybean lipid emulsions, we may reverse or prevent the progression of PN associated cholestasis and thus allow the patient to be maintained on adequate PN until they are able to ingest adequate nutrition enterally.

# PHASE II CLINICAL TRIAL HYPOTHESIS

The administration of Omegaven® in place of conventional phytosterol/soybean lipid emulsions will be safely provided to children with intestinal failure (defined as inability to wean from PN, with causes including short bowel syndrome) and PNALD and will reverse or prevent the progression of PN associated cholestasis and will allow the patient to be maintained on adequate PN until they are able to ingest adequate nutrition enterally.

#### SPECIFIC AIMS/OBJECTIVES

- To determine the impact of Omegaven® on reversal of conjugated hyperbilirubinemia
- To determine the impact of Omegaven® on the prevention of essential fatty acid deficiency
- To determine the impact of Omegaven® administration on serum triglyceride
- To determine the impact of Omegaven® administration on coagulation profiles

#### BACKGROUND AND SIGNIFICANCE

Parenteral Nutrition Associated Liver Disease (PNALD)

Parenteral nutrition (PN) provides intravenous nutritional supplementation for patients unable to absorb adequate enteral nutrients secondary to insufficient intestinal length or function. PN contains the macronutrient building blocks of the human diet in their most elemental forms (amino acids and dextrose) and is commonly administered with a lipid emulsion to avoid essential fatty acid deficiency and to provide a calorically dense source of non-protein calories. In addition, PN contains the essential micronutrients (electrolytes, trace elements, and vitamins) to provide an optimal nutritional regimen. Before the development of PN in the late 1960's, patients with insufficient gastrointestinal absorptive function commonly died of starvation and subsequent complications of malnutrition (1, 2). Today, more than 30,000 patients are permanently dependent on PN for survival. However, PN continues to be associated with hepatic injury that occurs at an unpredictable rate and includes both biochemical, i.e., elevated serum aminotransferase and alkaline phosphatase, and histologic alterations such as steatosis, steatohepatitis, lipidosis, cholestasis, fibrosis, and cirrhosis (3, 4). These abnormalities, which may worsen with the duration of PN administration, are more prevalent in the pediatric population. Additional risk factors for this condition include prematurity, low birth weight, long-term use of PN, the lack of concomitant enteral intake, systemic infections, and multiple operative procedures(5).

Although the pathological features of PN-induced liver injury have been well described, the etiology, prevention, and treatment of this complication are not well understood. Multiple hypotheses exist to explain the pathogenesis of PN-induced liver injury including altered gut hormonal profiles (6), the propensity for bacterial translocation in the absence of enteral intake (7, 8), intestinal stasis resulting in the reduced clearance of hepatotoxic bile acids (8), and direct deficiencies or toxic components of the PN solution itself resulting in excessive glucose calorie uptake, excessive lipid infusion, or nutritional deficiencies such as essential fatty acid deficiency (9-11). None of these theories has been confirmed consistently. The etiology of PN-associated liver disease is currently considered multifactorial. Available treatment options for this disease process are limited and have achieved moderate success at best. Care of the PN-dependent patient is focused on gradually increasing enteral caloric intake as the residual bowel adapts allowing PN to be discontinued (12). In fact, it has been shown both experimentally and clinically that partial enteral nutrition, when tolerated, helps to protect against the development of PN-associated liver injury (13-15). In severe cases of refractory hepatic failure, liver transplantation with or without accompanying small bowel transplantation remains the only treatment option.

#### Role of Intravenous Fat Emulsion on PN Associated Liver Disease

Recent evidence demonstrates that lipids are metabolized differently depending on their route of administration. Enteral lipids are absorbed by the enterocyte in the small bowel mucosa in the form of a micelle and packaged into chylomicrons which are released into the portal venous system for ultimate uptake and disposal in the liver. Once in the bloodstream, these particles rapidly acquire apolipoproteins from circulating high-density lipoproteins and can subsequently be metabolized by the liver. The emulsified particles of commercially made and intravenously administered lipid emulsions, such as Intralipid®, mimic the size and structure of chylomicrons, but differ in their content. In contrast to chylomicrons, artificial lipid particles primarily contain essential fatty acids and omega-6 triglycerides and are devoid of cholesterol or protein. Recent studies suggest that these omega-6 fatty acid-containing emulsions are dependent on lipoprotein lipase, apolipoprotein E, and low-density lipoprotein receptors for clearance, and are metabolized with less lipolysis and release of essential fatty acids than are chylomicrons. In fact, it appears that they may be cleared as whole particles by tissues other than the liver.(16) These factors may account for the increased incidence of steatohepatitis associated with the intravenous administration of Intralipid®.

The mechanism of clearance of omega-3 fatty acid containing lipid emulsions is unknown, but appears to be largely independent of the pathways identified above (17). Furthermore, omega-3 fatty acid solutions have been shown to decrease de novo lipogenesis (18), prevent or attenuate PN-induced hepatosteatosis in rats (19) and guinea pigs, and ameliorate the severity of high-fat diet-induced hepatosteatosis in rats (20). In addition, omega-3 fatty acids can interfere with the arachidonic acid pathway of inflammation (18, 21). They can displace arachidonic acid from tissue fatty acid pools, thereby reducing the availability for eicasanoid-synthesizing enzymes and inflammation (21).

Table 1 summarizes the composition of Intralipid® and Omegaven fat emulsions.

#### Rationale for Omegaven® Treatment

Unlike conventional intravenous fat emulsions, Omegaven® is comprised solely of fish oils containing primarily omega-3 fatty acids. Animal studies have shown that IV lipid emulsions such as fish oil that are high in eicosapentaenic and docosahexaenoic acid reduce impairment of bile flow as seen in cholestasis caused by conventional fat emulsions(19,20). By administering Omegaven® in place of conventional phytosterol/soybean fat emulsions, the cholestasis may be reversed and patients will be able to be maintained on adequate PN until they are able to ingest adequate nutrition enterally.

#### PRELIMANARY STUDIES/PROGRESS REPORT

**Animal Studies** 

The development of PN-associated liver injury may be dependent on both the route and quantity of lipid administration. Also, omega-3 fatty acids are thought to prevent or reduce de novo lipogenesis and the subsequent liver injury independent of the route of administration. Specifically, a previously established murine model of PN-associated liver injury was used to investigate whether enteral lipid administration would protect against the development of steatohepatitis in PN-dependent animals. In this murine model, steatohepatitis is largely due to a high carbohydrate load and essential fatty acid deficiency. Although this model is not replicative of the clinical setting, it is a model that maximizes liver steatosis. In this model, mice are treated with oral PN for 19 days before being sacrificed. These animals develop severe fatty liver changes demonstrated by MRI spectroscopy and histology (H&E, PAS, and oil red O staining), and also have biochemical changes consistent with liver injury (elevated alkaline phosphatase and serum transaminases). Experimental groups were supplemented with Intralipid® by several routes of administration including orally, intravenously, and subcutaneously. Other groups were also supplemented with omega-3 fatty acids (Omegaven®) by the same routes of administration. This study found a consistent pattern of protection against PN-associated steatohepatitis by administering enteral Intralipid® (22). In mice that received the highest dose of enteral Intralipid®, there was a marked decrease in the extent of overall liver injury as measured by gross inspection, histologic analysis, liver fat content, and serum liver enzyme levels. In all areas of this investigation, mice treated with enteral lipid most closely resembled the control mice that did not receive PN as part of the experimental protocol. These results were in complete contrast to the extensive fatty infiltration and evidence of hepatic injury found in mice that received PN without lipid supplementation, as well as in mice that received PN with intravenous Intralipid®. Mice receiving intravenous Intralipid® had the most severe liver changes. Both groups of animals developed marked hepatic steatosis with macrovesicular fatty infiltration and significant elevations in spectroscopic liver fat content and serum transaminase levels. In addition, the effect of enteral Intralipid® supplementation appeared to be dosedependent; mice receiving one-third the dose of enteral Intralipid® showed improved liver histology but still demonstrated a moderate degree of liver injury by spectroscopy and serum liver function tests.

The nutritional model employed in this study provided all experimental mice with enteral PN solution ad libitum. In this way, mice were not force-fed PN and self-regulated their PN intake by demands for growth and energy. Importantly, all mice gained weight throughout the 19-day protocol, and there were no differences in weight gain parameters between the groups. The PN solution was a typical pediatric stock containing 20% dextrose and 2% amino acids. Each milliliter of this formula provides 0.2 g (0.68 kilocalories) of dextrose and 0.02 g (0.08 kilocalories) amino acid. As the daily intake per animal of PN averaged 15 ml, mice were ingesting approximately 11.4 kilocalories/day and 456 kilocalories/kg/day. This caloric load is similar to the established dietary energy needs of the mouse (23). The parenteral fat source used in this study was Intralipid® 20% (Baxter, Deerfield, Illinois), which is a soybean oil-based emulsion. Each milliliter of this emulsion contains 0.2 g (2.0 kcal) of fat. It is recognized that the model may not completely match the clinical, human setting of intravenous PN-administration; however, the goal was to produce a fatty liver with biochemical evidence of injury.

In a second set of experiments, the same murine model was used to determine whether Omegaven®, a commercial fish oil emulsion available in Europe, would prevent fatty liver changes by enteral or parenteral routes of administration, and to determine the serum fatty acid profile of these animals. Animals receiving Omegaven® via the oral and intravenous routes had completely normal livers on histology and MRI spectroscopy revealed normal liver fat content. Liver functions tests in orally treated animals were also within the norm, while there were minimal elevations in intravenously treated groups. There was no fatty acid deficiency in these groups as determined by Mead acid (5, 8, 11-Eicosatrienoic acid) levels in the serum fatty acid analysis. Mead acid is the only polyunsaturated fatty acid of note produced de novo by animals and only accumulates under the conditions of essential fatty acid deficiency. Furthermore, arachadonic acid levels were low in Omegaven® treated animals consistent with previous reports. In a third set of experiments, mice were made severely fatty acid deficient. These mice were treated for 10 days with Omegaven® and had complete reversal of their fatty acid deficiency.

Similarly, other investigators studied livers in a newborn pig model and showed that intravenous administration of fish oil, which consists primarily of omega-3 fatty acids, reduced parenteral nutrition-induced cholestasis.(22) However, the study was only 3 weeks in duration and long-term effects from administration of omega-3 fatty acids alone were not evaluated. In fact, the idea that one could remove an essential fatty acid from the standard regime of nutritional support by PN has not been accepted. It has been thought that reduction of an essential fatty acid, such as omega-6, during long-term therapy would result in fatty acid deficiency and deterioration of the health of the patient. The Children's Hospital Boston's experience to date, demonstrates that the use of Omegaven® as monotherapy does not result in the development of essential fatty acid deficiency and it can actually be used to as monotherapy to treat this deficiency state.

Preliminary Safety and Efficacy Data for Use of Omegaven® in Other Diseases

Omegaven® has been used for over 10 years as an adjunct to conventional fat emulsions. According to current data, an increase in the proportion of omega-3 fatty acids is thought to optimize nutrition in general, but in particular benefit patients whose underlying disease might benefit from an increase in omega-3 fatty acids. An adequate intake of omega-3 fatty acids results in anti-inflammatory and immunomodulatory effects that are protective in nature from inflammatory tissue damage, capillary permeability, and improved immunological resistance. It may also reduce the risk of thrombosis and increase microvascular perfusion due to its anti-aggregatory and vasodilatory effects.

In Europe and Asia, the use of parenteral omega-3 fatty acids has been used in the following adult patient populations (24-28):

- Post traumatic and post surgical patients
- Patients experiencing early stages of sepsis/SIRS
- Patients at risk of hyperinflammatory processes
- Patients with inflammatory bowel disease (Crohn's disease, ulcerative colitis)

- Patients with inflammatory skin diseases (psoriasis, atopic eczema)

The dosing used in these patients was 0.1 g (1 ml) to a maximum of 0.2 (2 ml) /kg body weight. The infusion rate used did not exceed 0.5 ml/kg/body weight/hour. Since it was intended to be infused in combination with conventional fat emulsions, the total fat intake was limited to 10-20% as fish oil. The duration of administration did not exceed 4 weeks.

Preliminary Safety and Efficacy Data for Use of Omegaven® in Infants

Initial pediatric experience with Omegaven® was limited to 2 unpublished clinical trials (see reference). These trials were performed in Germany and Taiwan (29). The German study was a controlled, randomized, open parallel-group clinical study to investigate whether or not omega-3 fatty acids could be incorporated into the plasma phospholipids of very low birth weight preterm infants. In this 7-day safety trial, Omegaven® use was evaluated on the basis of clinical, laboratory, and antioxidant parameters and lipid metabolism. Treatment was started on day 3-5 of life and continued for a total of 7 days. Patients received Omegaven® plus conventional soybean fat emulsion or soybean emulsion alone. The maximum dose of Omegaven® in the study was 0.2 gm/kg/day. The study concluded that the Omegaven® was well tolerated in this group of preterm infants in respect to both hematological and biochemical parameters. The incidence of reported adverse events between both study groups was similar. The eicosapentaenoic acid (EPA) content of plasma phospholipids increased significantly in the Omegaven® arm, with the proportion of EPA to the total fatty acids reaching almost three times the baseline value. The sum of omega-3 fatty acids showed a significantly greater increase in the Omegaven® group compared to the conventional treatment arm.

The Taiwanese study was a single center, controlled, open-labeled study conducted to investigate the safety of parenteral administration of Omegaven in preterm infants. The group of 20 infants were randomized to one of two treatment groups; one consisting of Omegaven®/conventional lipids and the other consisting of conventional lipids alone. The average dose of Omegaven® in the treatment group of this 14-day study was 0.13 + 0.02 g/kg/day. There were no significant differences between the two groups with regard to body weight and length. Similarly, there was no significant difference in the hematological or biochemical parameters. There were no adverse events that were attributable to Omegaven® use. It was concluded that Omegaven® was well tolerated in these preterm infants.

In a recent article by Lee et al, entitled "Impact of fish oil-based lipid emulsion on serum triglyceride, bilirubin, and albumin levels in children with parenteral nutrition-associated liver disease", published in Pediatric Research (December, 2009), the authors demonstrated that substituting fish oil-based lipid emulsion for the standard soybean-based emulsion will result in normalizing, to some degree, the altered physiologic balance that comes to exist in patients dependent on PN. The indices that have shown improvement were decreasing direct bilirubin and triglyceride levels and increasing albumin levels. In previous publications, these authors have also noted that the provision of fish-oil-based fat emulsion was not associated with essential fatty acid deficiency, hypertriglyceridemia, coagulopathy, infections, or growth delay.

Researchers at The Hospital for Sick Children, Toronto, Canada published their findings of their experience with Omegaven® in young children in a recent publication (February, 2009) The median age was 7.5 (range 3.6-46) months, and median parenteral nutrition duration before starting Omegaven® was 28.4 (range 15.3-55.3) weeks. Median initial serum conjugated bilirubin was 137 (range 54-203) micromole/L (8.06 [3.18-11.94] mg/dL). Nine of the twelve patients had complete and sustained resolution of hyperbilirubinemia within a median of 24 (range 7-37) weeks, and all were no longer being considered for liver transplantation. Improvements in markers of hepatic inflammation as well as nutritional status also were noted in these patients. Three of the 12 patients received a liver-intestine transplant while taking Omegaven®. There were no complications attributable to Omegaven®.

## **DESIGN AND METHODS**

## Study Design

This phase II clinical trial will be a non-randomized, open-labeled, prospective study of intravenously administered Omegaven® fat emulsion in the treatment of PN associated liver injury.

# Patient Selection and Inclusion/Exclusion Criteria

After the diagnosis of PN liver injury is made, patients who are followed by the Neonatology, Gastroenterology, Surgery, or the Critical Care Service in conjunction with the patient's primary physician will contact [name], and an evaluation will be performed. If the patient's parents or guardians agree to participate in the study, informed consent will be obtained. The history of present illness and past medical history will be reviewed with the guardian and pertinent demographic and medical information will be recorded on data collection forms. These forms will be used to record all laboratory results, nutritional history, and descriptions of any liver biopsies performed.

Though most patients receiving parenteral nutrition do not develop end stage liver disease, there is a small percentage of patients, typically infants and children on prolonged courses of parenteral nutrition, who do go on to develop fulminant liver failure. The study population of this protocol is limited to patients felt to fulfill the following conditions:

- a) The patient will be PN-dependent (unable to meet nutritional needs solely by enteral nutrition) and
- b) The patient will have significant hepatic dysfunction due to PN despite utilization of all conventional therapies (the patient must have failed standard therapies to prevent the progression of his/her liver disease including surgical treatment, cycling of PN, reduction/removal of copper and manganese from PN, advancement of enteral feeding, and the use of ursodiol).

#### Inclusion Criteria:

- 1. Children 0-18 years of age
- 2. Patients will be PN-dependent and expected to continue PN for at least 30 days
- 3. Patients considered eligible for study participation must have PN-associated liver diseases. Other causes of liver disease (i.e., biliary atresia, galactosemia, alpha-1 antitrypsin deficiency) will be excluded. A liver biopsy is not necessary for treatment
- 4. Direct bilirubin > 2.0 mg/dl
- 5. Signed patient informed consent
- 6. Signed patient assent where applicable.

The patient will be hospitalized at the time of enrollment and initiation of Omegaven®.

#### Exclusion Criteria:

- 1. Pregnancy
- 2. Other causes of chronic liver disease (cystic fibrosis, biliary atresia, alpha-1 antitrypsin deficiency)
- 3. Signs of advanced liver disease including cirrhosis on biopsy, varices, ascites
- 4. The patient is allergic to eggs/shellfish
- 5. The patient has a severe hemorrhagic disorder
- 6. The patient is enrolled in any other clinical trial involving an investigational agent (unless approved by the designated physicians on the multidisciplinary team)
- 7. The parent or guardian or child unwilling to provide consent or assent.

# **Screening Procedures**

Prior historical and physical information, imaging studies, biopsies, and other available specialized tests will be reviewed by the multidisciplinary team experienced in the diagnosis and treatment of parenteral nutrition associated liver disease. Additional biochemical monitoring will be performed as necessary. If the patient's status supports consideration of treatment, the option for non-experimental therapy will be investigated.

# **Recruitment Methods**

With an anticipated enrollment of 3-5 patients per year, 20-25 patients will be recruited over the course of the 5 year study.

Patients in the trial will be recruited from the NICU, PICU, CVICU, surgery, gastroenterology, and general pediatrics services at Levine Children's Hospital (LCH). Approximately 5-8 patients/year are diagnosed with severe PN associated liver injury at Levine Children's Hospital. The Principal Investigator ([name]) or Co-investigators ([name], [name]) will discuss treatment options including study treatment with the parents or legal guardians. Informed consent for participation in the study will only be obtained by physicians who are able to fully inform the patients of alternatives to participation. If the patient is a minor but of sufficient age and understanding, patient assent will also be obtained.

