#### **Duration of Therapy**

Patients will complete the study when he/she is completely off PN; develops a contraindication for further use; or the patient/family requests to be removed from the study protocol.

In the event that a patient who has been listed for a liver or liver/intestinal transplant has an organ become available, the participation in this protocol will not preclude them from receiving the transplant. Omegaven® will not be administered post transplant.

In the event that a patient whose hepatic enzymes and serum bilirubin have normalized still requires parenteral fat emulsion after receiving Omegaven® for more than 6 months, their clinical course will be reviewed, and a decision will be made whether to continue the Omegaven® or rechallenge the patient with conventional therapy (Intralipid®).

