# **Discontinuation of Therapy**

Patients will continue to be followed by the Nutritional Support Program (LCH Division of Gastroenterology) upon discontinuation of therapy with Omegaven® a minimum of 3 months after the treatment is stopped. In addition, patients will be contacted annually for 5 years following completion of the study, to ascertain growth, well being and PN dependency.

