# **Definition of Primary and Secondary Outcomes/Endpoints**

The primary outcome is normalization of direct bilirubin to less than 0.4mg/dL by 9 months.

Seconday outcomes include:

- Omegaven® will prevent EFA deficiency as evidenced by normal EFA profiles on monthly evaluations
- The rate of triglyceride levels > 400 mg/dL with Omegaven® will be similar to that seen with PN administered with soy oil IFE (conventional emulsion, i.e., Intralipid®) as evidenced by baseline data and then weekly and monthly evaluations
- PN containing Omegaven® will be safe for patients with respect to the risk of unexpected bleeding/coagulopathies as evidenced by weekly and monthly evaluations

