# **Study Protocol Timeline**

This study protocol will end five years following commencement of the study.

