# **Statistical Power and Sample Considerations**

As discussed above, this study protocol is not intended to prove statistical significance.

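### An enrolment rate of 3-5 patients per year over 5 years gives 15-25 patients, not the stated 20-25; the last-enrolment date relative to the 9-month outcome also needs clarifying

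*Protocol*

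**What the plan says.** Recruitment Methods gives the rate, the duration and the total in one sentence: "With an anticipated enrollment of 3-5 patients per year, 20-25 patients will be recruited over the course of the 5 year study". The same section describes the local caseload: "Approximately 5-8 patients/year are diagnosed with severe PN associated liver injury". In the protocol text available for review, this is the only statement of sample size. Statistical Power and Sample Considerations derives no number and says that "this study protocol is not intended to prove statistical significance".

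Three other sections bear on the calendar:

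- Study Protocol Timeline: "This study protocol will end five years following commencement of the study".
- Definition of Primary and Secondary Outcomes/Endpoints: "The primary outcome is normalization of direct bilirubin to less than 0.4mg/dL by 9 months".
- Duration of Therapy lists the events that complete a patient's participation, beginning "Patients will complete the study when he/she is completely off PN; develops a contraindication for further use" and ending with a request by the patient or family. Calendar closure of the study is not among them.

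Discontinuation of Therapy adds at least 3 months of follow-up after treatment stops, and then says that "patients will be contacted annually for 5 years following completion of the study, to ascertain growth, well being and PN dependency". It names no bilirubin measurement. No last-enrolment date and no minimum follow-up of 9 months is stated.

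**The concern.** The sentence presents the total as following from the rate, but the low end of the total does not follow. A reader who takes 20 as the planned minimum would expect 5 more patients than the protocol's own low forecast supplies. What is at stake is the expected size of the study, and so the precision with which the proportion reaching normal bilirubin will be estimated. No hypothesis test depends on it.

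The calendar raises a smaller, conditional question. If enrolment stays open to the end of year five, a child who enters after month 51 reaches month 60 with less than 9 months on study. The protocol does not say whether that child's bilirubin will still be collected for the primary outcome up to 9 months.

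**Working it through.** **Inputs**

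- Rate: 3 to 5 patients per year (Recruitment Methods).
- Recruitment period: 5 years (Recruitment Methods).
- Stated total: 20 to 25 (Recruitment Methods).
- Primary outcome window: 9 months (Definition of Primary and Secondary Outcomes/Endpoints).
- Study end: 60 months after commencement (Study Protocol Timeline).

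**Step 1. Reproduce the stated total** as rate × years.

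| | Calculation | Result | Stated | Agrees? |
|---|---|---|---|---|
| Low end | 3 × 5 | 15 | 20 | No |
| High end | 5 × 5 | 25 | 25 | Yes |

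The low end differs by 20 − 15 = 5 patients, which is 5/20 = 25% of the stated minimum.

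**Step 2. What the stated minimum would need.** Rate for 20 patients in 5 years: 20/5 = 4 per year. Time for 20 patients at 3 per year: 20/3 = 6.7 years.

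**Step 3. Effect on precision.** The measure is the largest half-width of the exact (Clopper-Pearson) 95% interval for a proportion, taken over all possible outcomes.

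| n | Widest half-width |
|---|---|
| 13 | 0.278 |
| 15 | 0.261 |
| 20 | 0.228 |
| 21 | 0.223 |
| 25 | 0.204 |

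Going from 20 to 15 patients widens the interval from about ±23 to about ±26 percentage points.

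**Step 4. The calendar.** The last entry month that allows 9 months before month 60 is 60 − 9 = 51. Assume accrual is even to month 60; the protocol does not state this.

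- Share entering after month 51: 9/60 = 15%.
- Number: 0.75 × 3 = 2.25 to 0.75 × 5 = 3.75, about 2-4 children.
- Ceiling on the effect: the primary proportion differs between counting all of them as failures and all as successes by 2.25/15 = 3.75/25 = 0.15, or 15 points. The true gap is smaller, because the outcome is normalization *by* 9 months and a child who normalizes before closure is observed to do so.

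**Step 5. If enrolment closed at month 51** (51/12 = 4.25 years).

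- Expected accrual: 3 × 4.25 = 12.75 to 5 × 4.25 = 21.25, about 13-21.
- Rate needed for 20-25: 20/4.25 = 4.7 to 25/4.25 = 5.9 per year, which is above the stated range except for the part from 4.7 to 5.

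**The case against.** **On the total.** The rate is only anticipated, 20-25 lies inside 15-25, and 20 is what the midpoint rate of 4 per year delivers. The site diagnoses 5-8 children per year, or 25-40 over 5 years, so the caseload does not rule out 20-25. All of this stands. A reader might infer that the target cannot be reached, and the documents do not support that. But the caseload figure counts diagnosed children, not children who are eligible and consent, so it cannot replace the protocol's own enrolment forecast. That forecast still starts at 3 per year, and the sentence still does not add up at its low end.

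**On consequences.** Nothing formal depends on the number. The interval widths above describe the cost of a smaller minimum; they do not show that a precision target was missed, since none is set. This also stands, and it is why the point is minor.

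**On the calendar.** A reader might infer that the protocol contradicts itself, or that 15% of primary outcomes will be lost. Neither follows. The recruitment, timeline and outcome statements can all be true together. Calendar closure is not listed as completing a patient's participation, and contact after treatment and after study completion is planned, so the five-year end need not be a hard data cut-off. If the 3-month follow-up after treatment supplied a bilirubin value (an assumption, since none is named), only entrants after month 54 would be affected: 6/60 = 10%, or 0.5 × 3 = 1.5 to 0.5 × 5 = 2.5 children. How incomplete follow-up is handled in the analysis may also be set out in an analysis plan not shown here. What remains is an unstated date, which calls for a clarification.

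**Conclusion.** The arithmetic point holds as written and needs no assumption: the stated rate over the stated period gives 15-25, and the lower bound of 20 is overstated by 5 patients relative to that rate. It is minor, because no power target, precision target or decision rule uses the figure.

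The calendar point holds only as a request for clarification. Its size depends on enrolment continuing past month 51. With even accrual to month 60 (assumed), at most 15% of entrants, about 2-4 children, would have under 9 months on study at closure. Fewer would have an unknown outcome, since those who normalize before closure are observed.

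**What to change.** **Main change.** In Recruitment Methods, either state expected accrual as 15-25, or keep 20-25 and restate the rate as 4-5 per year. The first option means a less favourable stated minimum: a widest half-width of about 26 points at 15 patients against 23 at 20. The second commits the site to a higher minimum rate.

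**Clarification.** State one of the following, and reconcile Study Protocol Timeline, Duration of Therapy and Discontinuation of Therapy with it:

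- Enrolment closes at month 51. The five-year end is kept, but expected accrual at 3-5 per year falls to about 13-21, with a widest half-width of about 28 to 22 points. The 20-25 total cannot be kept alongside this at the stated rate.
- Bilirubin follow-up for the primary outcome continues to 9 months for the last child enrolled. Accrual is unaffected, but data collection may end up to 9 months later, and a child already off treatment may need a 9-month bilirubin that the protocol does not now name.

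The main change is a correction of wording. The second clarification option goes further, because it extends data collection. Either is a protocol change that, under the protocol's Legal and Ethics Requirements, needs review and approval before it is implemented.
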